### **3) Objectives\***

This is a 24-week, randomized, double-blind, placebo-controlled trial of exenatide weekly injection (2mg per dose) as an adjunctive therapy in 70 schizophrenia subjects to examine exenatide's effects on negative symptoms and cognition.

Primary aim: Examine the efficacy of exenatide weekly injection in improving negative symptoms as measured by the Scale for the Assessment of Negative Symptoms (SANS) total score.

Secondary aims: Examine the efficacy of exenatide in improving cognition as measured by the MATRICS Consensus Cognitive Battery (MCCB) composite score.

Tertiary/exploratory aims:

1. Examine exenatide's effect on schizophrenia symptoms as measured by the Positive and Negative Syndrome Scale (PANSS) total score.
2. Examine the efficacy of exenatide in improving social function as measured by the Instrumental Activities of Daily Living Scale (IADL) and the Heinrichs Carpenter Quality of Life Scale (QLS).
3. Examine exenatide's effect on neuro-protection as measured by the change in hippocampal volume.
4. Examine exenatide's effects on inflammatory markers including serum levels of high sensitivity CRP, IL-6, and TNF- $\alpha$ .
5. Examine the potential moderator role of baseline serum levels of CRP, IL-6, TNF- $\alpha$ , and baseline hippocampal volume for exenatide's effects on negative and cognitive symptoms.
6. Examine the potential mediator role of changes from baseline in serum levels of CRP, IL-6, TNF- $\alpha$ , and hippocampal volume for exenatide's effects on negative and cognitive symptoms.
7. Examine the efficacy of exenatide in reducing body weight and improving glucose metabolism as measured by fasting plasma glucose and HbA1c.
8. Examine the safety and tolerability of exenatide as measured by changes in the side effects questionnaire (SEQ, SEQabbrev), EKG and vital signs

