## 6) Study-Wide Number of Subjects\*

This is a single site study. We expect to enroll 110 subjects in this study with the goal of randomizing 70 subjects.

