## **9) Study Endpoints\***

### Primary Study Endpoint:

Improvement in negative symptoms as measured by the Scale for the Assessment of Negative Symptoms (SANS) total score.

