### Secondary Study Endpoint:

Improvement in cognition as measured by the MATRICS Consensus Cognitive Battery (MCCB) composite score.

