
Baseline visit: The baseline visit will take about 5 hours to complete. Eligible subjects will come to the clinic for the baseline visit. Subjects will complete the clinical symptoms assessment, the extrapyramidal symptoms (EPS) assessment, and vital signs. On a separate day, subjects will come to the UMass Imaging Center at the university campus, or UMass Memorial MRI & Imaging Center at Shields MRI Imaging Suite to complete the brain MRI scans. Then the subjects will receive the study medication (either exenatide weekly injection (2mg per dose) or placebo injection). The UMass research pharmacy is responsible for randomization and preparation of study medication. The randomization is based on a double-blinded 1:1 ratio using permuted block randomization with randomly varying block size.

Follow-up visits (week 1-23): These visits will take about one hour to complete. Subjects will come to the clinic weekly to receive the study medication injection (exenatide or placebo); possible side effects will be assessed weekly. At week 6, 12, 18 visits, vital signs, the clinical symptoms assessment and the EPS assessment will be repeated; fasting blood samples for glucose, insulin, HbA1c, lipid profile, comprehensive metabolic profile, CBC, high sensitivity

CRP, eGFR and TNF- $\alpha$  will be obtained. In the event that research staff are unable to obtain a subject's blood sample at an indicated visit, subject's blood will be drawn in a week's time by a professional phlebotomist at UMass. In the event that a subject misses a visit where a routine blood draw is required, the subject will be scheduled to complete the routine blood draw prior to receiving the next dose of study medication. Once the lab results have been reviewed and signed off by the PI, the subject will be scheduled for their next study visit and will resume receiving the study medication.

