## **12) Data Management\***

All data management will be conducted in the research offices of the Biotech One building. Standard data forms for the clinical rating scales will be used for this project. Individual notebooks will be maintained for each subject that will include signed consent, letter to halfway house, subject information sheets, raw data from clinical rating scales, laboratory measurements and a study timetable or flow sheet for that subject. A study database will be created using the REDCap system. The data will be stored on a secure server in the UMass HIPAA-compliant data center with daily backup. The database will be designed by the PI and maintained by the PI and the research staff. Data entry will be performed by research coordinators and will be reviewed by the research manager and the PI for accuracy. Access to the database will be restricted by password. All data will be stored safely for 5 years.

There are no published data yet about exenatide's effects on clinical symptoms and cognition in the schizophrenia population. This study is intended as an initial test of efficacy. Repeated measures of clinical symptoms and cognitive performance will be analyzed in separate linear mixed models with fixed effects of visit, treatment group, baseline score, and visit x treatment and visit x baseline score interactions and random participant-specific intercepts and slopes. Potential confounding variables will be included as covariates. The effect of exenatide on 24-week change from baseline will be determined by the estimated regression coefficient of the visit x group interaction term. The sample of 60 evaluable subjects will have 80% power to detect an effect size of 0.74 based on a two-tailed t-test at alpha = 0.05.

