Statistical analysis: Statistical analysis was performed using SPSS (version 24.0, IBM Corp, Armonk, NY, USA). Descriptive statistics were performed to summarize demographic and clinical characteristics of the study sample. Group comparisons were performed using independent samples t test for continuous variables and the Fisher exact test or Chi-square test for categorical variables. The outcome measures were repeated at different time points. Therefore, analysis of repeated measures using mixed models was performed to compare the change over time in outcome measures between the two treatment groups while controlling for potential confounding variables. The mixed model approach does not require subjects to have the same number of study visits or measurements and uses all available data instead of eliminating subjects with missing data, resulting in unbiased estimates of the model parameters when data are missing at random. Further, for those who completed 24-week treatment, analysis of covariance (ANCOVA) was used to compare change scores from baseline to week 24 between the two treatment groups controlling for potential confounding variables. For all analyses, a P value less than 0.05 (two-tailed) was used for statistical significance.

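### The SAP applies one unadjusted 0.05 threshold to all analyses and names neither a primary outcome nor a deciding analysis, so the protocol's ranking of outcomes is not carried forward

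*SAP*

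**What the plan says.** The protocol is clear about rank. Section 9 gives one primary endpoint, "Improvement in negative symptoms as measured by the Scale for the Assessment of Negative Symptoms (SANS) total score", and one secondary endpoint, "Improvement in cognition as measured by the MATRICS Consensus Cognitive Battery (MCCB) composite score". Section 3 agrees ("Primary aim: Examine the efficacy of exenatide weekly injection in improving negative symptoms") and places eight further aims under a tertiary/exploratory heading. Section 12 specifies a mixed model for the repeated measures and takes the treatment effect on 24-week change from its visit-by-group term. The sample size rests on a single test: "The sample of 60 evaluable subjects will have 80% power to detect an effect size of 0.74", "based on a two-tailed t-test at alpha = 0.05". The protocol gives no testing sequence and no multiplicity adjustment.

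The SAP ranks nothing. SANS and MCCB appear among seven clinical scales in the description of visits, followed by three extrapyramidal (EPS) scales and an account of the assays. The statistical analysis paragraph speaks only of outcome measures. It compares them by mixed model and adds an ANCOVA of change scores in those who completed 24 weeks. It then states: "For all analyses, a P value less than 0.05 (two-tailed) was used for statistical significance".

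**The concern.** The last sentence is a stated decision rule, not merely silence about multiplicity. It covers every outcome and both analyses. Under it, MCCB, a depression score or a lipid fraction with a P value of 0.04 in either analysis is significant whatever happens to SANS. SANS itself has two routes to significance.

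This matters because the trial is small. It has 80% power only for a standardised effect of 0.74, so SANS could easily miss significance even if a moderate effect exists. A report with a null primary and a few scattered results below 0.05 is then quite possible, and the SAP gives the reader no basis for weighing those results differently from the primary.

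**Working it through.** **Inputs from the documents.** Two-sided alpha 0.05 for all analyses (SAP, statistical analysis). 60 evaluable subjects, effect size 0.74, 80% power (protocol section 12). 1:1 allocation (protocol section 10), hence 30 per arm.

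**Inputs assumed.** The SAP does not list its tests, and neither document gives correlations. I take a common correlation r between outcomes from 0 to 0.7, a correlation of 0.9 between the mixed-model and ANCOVA tests of the same outcome, and every null true.

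**1. The plan's own figure.** Noncentrality = 0.74 × √(30/2) = 0.74 × 3.873 = 2.866. With 58 degrees of freedom the critical value is 2.002, and power from the noncentral t distribution is 80.5%. The stated 80% is reproduced. By the same formula an effect of 0.5 gives noncentrality 0.5 × 3.873 = 1.936 and power of about 48%.

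**2. SANS alone.** One analysis: 5%. If either of two analyses with correlation 0.9 may count, the chance that at least one falls below 0.05 is about 7.0%. At correlation 0.8 it is about 7.8%.

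**3. SANS and MCCB, unordered.** One independent test each: 1 − 0.95² = 9.75%. At r = 0.5 this is about 9.0%. With two analyses each it is about 13.6% (r = 0) to 12.5% (r = 0.5).

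**4. The nine clinical and EPS scales other than SANS.** These are PANSS, CGI, CDSS, QLS, IADL, MCCB, Simpson-Angus, Barnes and AIMS. If independent, 1 − 0.95⁹ = 37.0%. With a common correlation (two-sided normal tests):

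| r | 0 | 0.3 | 0.5 | 0.7 |
|---|---|---|---|---|
| 9 outcomes | 37% | 33% | 27% | 20% |
| 20 outcomes | 64% | 54% | 42% | 29% |

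**5. Adding laboratory measures.** The 20 are those nine plus eleven assembled from the SAP's bioassay section: glucose, insulin, HOMA-IR, HbA1c, total cholesterol, triglycerides, HDL, LDL, hsCRP, IL-6 and TNF-α. If independent, 1 − 0.95²⁰ = 64.2%. These rows count one analysis per outcome; a second analysis raises them.

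**6. After the fix.** If SANS is tested once at 0.05 and MCCB is tested only after SANS succeeds, the chance of any false claim on the two is at most 5%. If the SANS null is true, an error requires a false rejection of SANS (5%). If it is not, only MCCB can be in error (at most 5%). The SANS test, its alpha and its power of about 80% are unchanged.

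**The case against.** The strongest reply is that the ranking still stands. The SAP does not revoke the protocol, which has one primary endpoint and labels the rest. Tested once, the primary has 5% error. Family-wise control over safety scales and exploratory laboratory values is not usual, least of all in a trial that the protocol describes as an initial test of efficacy and not intended to support a new indication. Much of this stands: the protocol's labels remain in force, and unadjusted exploratory tests are acceptable if they are labelled so. It does not answer the point, because the SAP's rule covers all analyses, does not label any of them, and leaves open which analysis tests SANS.

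A reader might infer that at least one false significant result is more likely than not. The documents do not support that. The number of tests is an assembly from the procedures text, not a list of planned comparisons. For 20 outcomes the figure passes from above 50% to below it within the correlations considered. The twelve outcomes named in the protocol's aims (SANS, MCCB, PANSS, IADL, QLS, hippocampal volume, CRP, IL-6, TNF-α, weight, glucose, HbA1c) give 1 − 0.95¹² = 46% even if independent. The all-null assumption also sits badly with the protocol's background (section 4), which cites effects of exenatide on glucose, lipids, hsCRP and IL-6; real effects are not false positives.

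Nor does the SAP declare every outcome significant. It sets a threshold, and says nothing about how a null primary would be presented.

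**Conclusion.** The point holds as a defect of the SAP's decision rule. The rule is unadjusted, covers all analyses, and names neither a primary outcome nor a deciding analysis, so followed literally it allows a claim on any outcome by either method when SANS fails.

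The firmest figures do not depend on how many laboratory measures are counted: about 7% rather than 5% for SANS if either analysis may count (assumed correlation 0.9), and up to 9.75% for SANS plus MCCB with one test each. The 20 to 37% for the nine other scales is conditional on all nulls being true and on the assumed correlations. The 29 to 64% for about twenty outcomes is an upper illustration only. The SAP should be corrected, but the protocol's choice of primary endpoint and its power are not in question.

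**What to change.** State in the SAP:

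1. SANS total at week 24 is the single primary outcome. It is tested at two-sided 0.05 by the protocol's mixed model, through the visit-by-group term. The completer ANCOVA is a sensitivity analysis and does not decide.
2. MCCB composite, by the same mixed model, is formally tested at 0.05 only if SANS is significant. Otherwise it is reported with a nominal P value. This gate is a new rule; the protocol ranks MCCB second but does not make its test conditional.
3. All other outcomes are reported as estimates with 95% confidence intervals and nominal P values, labelled exploratory.

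The cost is wording, plus the loss of a formal MCCB claim if SANS fails. Sample size, alpha and power for SANS do not change. The SAP is written in the past tense, so the analysis may already have been run. In that case the report should say that the ordering of outcomes comes from the protocol's ranking and that the MCCB gate was added later; the gate should not be presented as prespecified.
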